7.3. Other Analyses

7.3.1. Clinical Laboratory Test

Analysis Set: Full Analysis Set Analysis Variables: Glycoalbumin

1,5-AG

Fasting blood glucose

Fasting insulin

Fasting glucagon

Fasting proinsulin

Fasting GLP-1

Fasting GIP

DPP-4 Activity

Inhibitory Rate of DPP-4 Activity

Time Point: Start of the observation period, Week 3-4 of the treatment period (Day 1, Day 4-6, Day 9)

Analysis Methods: For the above analysis items, the following analysis is performed

(1) For measurement values and changes from start of the observation period, summary statistics and two-sided 95% CI by time point (each Day) will be calculated by treatment group. The time course will be presented graphically using the mean change and SD.

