7.4 Research Subject Management

The principal investigator and investigator shall instruct the research subject the items below.

- (1) Give instructions to take allocated oral hypoglycemic drug as directed. If poor compliance with study treatment (e.g., < 75% of the prescribed dose) after the previous visit has been found and does not improve, the research subject may be withdrawn from the research if appropriate for the circumstances.
- (2) If hypoglycemia symptom (hunger abnormal, feeling of weakness, trembling of hands and fingers, cold sweat, palpitations, etc.) is observed, take glucose or sucrose (sugar), and if it does not improve give instructions to visit promptly.
- (3) For dietetic therapy and exercise therapy (if performed), the principal investigator and investigator shall make sure prescriptions (instructions for calories, etc.) are consistent throughout the research period, and instruct the research subject to adhere to the dietetic therapy and exercise therapy (if performed).

- (4) When CGM is being conducted, the principal investigator and investigator shall instruct exercise therapy (if performed) that may be performed under the same conditions every day, and instruct the research subject to adhere to it.
- (5) When CGM is being conducted, give instruction to photograph every meal contents.
- (6) Instruct the research subject not to eat high-sugar, high-calorie food or beverage between meals during CGM.
- (7) When CGM is being conducted, give instructions to note necessary items into the research subject diary.
- (8) On visit days for planned laboratory tests, give instructions not to take oral hypoglycemic drug scheduled to be taken on that day. Further, at each visit, have the research subject report if drug has been taken or not the day before, and on the day of visit.
- (9) On visit days for planned laboratory tests, give instructions for fasting ≥ 10 hours before visit.
- (10) For research subjects of childbearing potential, give instructions to use adequate contraception. If pregnancy is discovered, have the research subject report promptly, and discontinue the research immediately.
- (11) The principal investigator and investigator shall instruct the research subject to adhere to instructed prohibited concomitant drugs. When drugs are taken other than the drugs prescribed by the principal investigator and investigator, have the research subject report its content.

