8.1.2 Dose and administration method

Trelagliptin 100 mg (once weekly) or alogliptin 25 mg (once daily) shall be administered orally before breakfast. However, the drug shall be administered as described below at the start of the treatment period (VISIT 2: Day 1) or during the treatment period (VISIT 3: Day 21).

At the start of the treatment period (VISIT 2: Day 1): The drug shall be administered after required tests/observations, etc.

During the treatment period (from VISIT 3 to VISIT 5):

Trelagliptin 100 mg/week group shall insert the sensor on a day between 3day and a day before Trelagliptin administration day. Trelagliptin 100 mg/week shall be administered before breakfast on the day of the drug administration. The next administration of Trelagliptin 100 mg is after the sensor removal.

Alogliptin 25 mg/day shall be administered after required tests/observations, etc at every VISIT without taking study drug. Research subjects shall take study drug prior to the every breakfast at home.

Duration of treatment shall be start of treatment period (Day 1) to end of treatment period (Day 29).

Dose and administration method for each administration group are shown in table 8.a.

Table8.a Administration group and administration method

Administration group	Dose	Route of administration:	Administration method
Trelagliptin group	Trelagliptin 100 mg	Oral	Once weekly, before
Tretagripuit group	Tretagnpun 100 mg	administration	breakfast
Alaslintin anaum	Alaalintin 25 ma	Oral	Once daily, before
Alogliptin group	Alogliptin 25 mg	administration	breakfast

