- Changes in AUC over time during periods when blood glucose < 70 mg/dL (hypoglycemia) is observed*1,2
- Change in peak postprandial glucose levels over time 3 hours after breakfast, lunch, and evening meal*1,2
- Change in maximum variation of blood glucose levels over time between before and after breakfast, lunch, and evening meal *1, 2
- Changes in MAGE*1, 2
- Changes in mean 24-hour blood glucose levels *1, 2
- Changes in mean daytime blood glucose levels*1,2
- Changes in mean nocturnal blood glucose levels*1, 2
- Changes in AUC*1, 2
- Changes in AUC over time during periods when blood glucose 110 mg/dL is observed*1,2
- Changes in the SD of 24-hour blood glucose values*1,2
- Changes in the SD of mean daytime blood glucose values*1,2
- Changes in the SD of mean nocturnal blood glucose values*1,2
 - *1: Measured value and percent changes for the each 7-day period between Week 3 and Week 4 (between Day 22 and Day 28) of the treatment period calculated from the value at the start of

the observation period (however changes in the SD of 24-hour blood glucose values shall be measured value only)

*2: Percent change from the value at the start of the observation period to the mean value during the 7-day period between Week 3 and Week 4 (between Day 22 and Day 28) of the treatment period

(Analysis method)

• Conduct the same analysis as the primary endpoints for *1 and *2 of the above endpoint section. However, for changes in mean/SD, only measured values of *1 and *2 shall be illustrated.

[Other endpoints]

- Glycoalbumin
- 1,5-AG
- Fasting blood glucose
- Fasting insulin
- Fasting glucagon
- Fasting proinsulin
- FastingGLP-1
- Fasting GIP
- DPP-4 activity
- Inhibitory rate of DPP-4 activity

(Analysis method)

Calculate summary statistics and 95% confidence interval (two sides) of mean at each
evaluation point (the start of the observation period by each treatment group, first day, 1 point
during third to fifth day, and ninth day of CGM which is to be performed for 9 days from Day
21) in measured values and changes from the start of the observation period, and illustrate
changes in mean and SD

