Appendix A Schedule of Research Procedures

		Observation period Treatment period						
Time of Visit	Week			0			4	Disconti nuation ^{(g}
	Day	-14	-2	1 ^(b)	21 ^(c)	24 ^(c)	29 ^(c)	-
Allowable ran	nge (Day)	-28 to -2	-4 to -2	1	19 to 35	24~39 ^(f)	29 to 43	-
VISIT Numb	er		1	2	3	4	5	-
Informed procedure	consent	×						
Inclusion/Exc criteria		×	×					
Demographic information		×						
Medical pre-treatment		×	×					
Physical exan		×	×	(\times)	×	×	×	×
Body weight,	BMI		×		×		×	X
Height		×						
Concomitant		×	×	(\times)	×	×	×	×
Concurrent di		×	×					
Laboratory te	sts ^(a)		×		×	×	×	×
HbA1c			×					
Drug -taking					×	×	×	X
Prescription of dietetic therapy and exercise therapy and assessment of compliance		×	×	(×)	×	×	×	×
CGM	-		× (d) (Sensor	(d) × (Sensor	× (d) (Sensor	× (d) (Exchange sensor)	(d) × (Sensor	
Self-measurer			insertion) × (e)	remove) × (e)	× (e)	× (e)	remove) × (e)	
Adverse even monitoring	t			×				

(a) Measured on VISIT1 (Day-2), and the first and ninth days of the 9-day CGM starting on Day 21

Blood tests: glycoalbumin, 1,5-AG, fasting insulin, fasting glucagon, fasting proinsulin, fasting GLP-1, fasting GIP*, DPP-4 activity Measured on 1 point during fourth and sixth day of the 9-day CGM starting on Day 21

Blood tests: fasting GLP-1, fasting GIP, DPP-4 activity

- (b) The starting day of study treatment in the treatment period is designated as Day 1. The study drug shall be administered after required tests/observations, etc. The day before the start of study treatment in the treatment period is designated as Day -1. It is performed at the visit when principal investigator or investigator consider as needed.
- (c) Trelagliptin 100 mg/week group shall insert the sensor on a day between 3 day and a day before Trelagliptin administration day. Trelagliptin 100 mg/week shall be administered before breakfast on the day of the drug administration.

Alogliptin 25 mg/day shall be administered after required tests/observations, etc at every VISIT without taking study drug. Research subjects shall take study drug prior to the every breakfast at home.

- (d) To be performed by study site personnel
- (e) At least, blood glucose levels shall be measured at three time points on the first day of CGM ([1] at least 2 hours after the recorder is connected and [2] 2 hours after the first is measured. [3] at bedtime) and at four time points from the second day onward ([1] before breakfast, (2) before lunch, (3) before evening meal, and (4) at bedtime).

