- (f) Research subjects should visit the study site on a day between fourth and sixth day of the 9-day CGM starting on Day 21.
- (g) To be performed to the extent possible

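### In the trelagliptin arm, the laboratory time points pool different days since the weekly dose, which blurs the weekly DPP-4, GLP-1 and GIP profile

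*SAP*

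**What the plan says.** The protocol file holds three versions. References here are to the current one, whose Visit 3 range is Days 19 to 35.

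- **Insertion relative to dose.** Protocol 8.1.2: "Trelagliptin 100 mg/week group shall insert the sensor on a day between 3day and a day before Trelagliptin administration day". Appendix A note (c) says the same. The lead is therefore 1, 2 or 3 days.
- **Sampling relative to insertion.** Appendix A note (a) puts the full panel on "the first and ninth days of the 9-day CGM starting on Day 21". The extra GLP-1, GIP and DPP-4 sample is "Measured on 1 point during fourth and sixth day of the 9-day CGM starting on Day 21". Note (f) sets Visit 4 the same way: "Research subjects should visit the study site on a day between fourth and sixth day of the 9-day CGM starting on Day 21". None of these sampling rules refers to the dose.
- **Order on a visit day.** Protocol 7.4, item 8: "On visit days for planned laboratory tests, give instructions not to take oral hypoglycemic drug scheduled to be taken on that day".
- **Analysis.** SAP 7.3.1 uses "Time Point: Start of the observation period, Week 3-4 of the treatment period (Day 1, Day 4-6, Day 9", and at each point "summary statistics and two-sided 95% CI by time point (each Day) will be calculated by treatment group". It has no variable for days since dose.
- **SAP time windows.** SAP section 2 gives reference dates for each laboratory time point, but these only choose between several evaluable values. For 'Day 4-6' it accepts any value from the day after insertion up to the ninth-day sample.
- **A different rule for glucose.** The CGM glucose windows in SAP section 2 are anchored to the dose that follows insertion.

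**The concern.** DPP-4 activity, its inhibitory rate, GLP-1 and GIP are the plan's direct evidence on whether enzyme inhibition holds across the weekly interval. That bears on the secondary objective of comparing once-weekly with daily administration. If one label holds samples from different days since the dose, the label means no longer trace the weekly course.

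Only trelagliptin is exposed to this. Alogliptin is taken daily, and after the tests at visits, so its on-treatment samples are always about 24 hours after the last dose. The spread at 'Day 1' and 'Day 9' also reaches the other fasting tests drawn on those days. With about 15 subjects per arm, a few differently timed samples can shift a mean. Laboratory day labels also fail to line up with the dose-anchored glucose days when the lead is 2 or 3.

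**Working it through.** **Inputs.** Weekly dosing (Protocol 8.1.2) gives nominal doses on Days 1, 8, 15, 22, 29 and 36; no slippage is assumed. Lead k = 1, 2 or 3 (8.1.2, Appendix A note c). Samples fall on CGM day c = 1, one of 4 to 6, and 9 (Appendix A notes a and f). On a dose day the sample precedes the drug (7.4, item 8). Allowable ranges (Appendix A): Visit 3, Days 19 to 35; Visit 4, Days 24 to 39; Visit 5, Days 29 to 43.

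**Step 1: reproduce the plan's Visit 3 range.** Insertion day = dose day − k, for doses on Days 22, 29 and 36. Earliest: 22 − 3 = 19. Latest: 36 − 1 = 35. This matches the stated range exactly, which supports reading the lead as 1 to 3 days.

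**Step 2: days since the last dose.** The dose falls on CGM day k + 1. For c > k + 1, days since dose = c − (k + 1). For c ≤ k + 1 the last dose is the previous one, so add 7.

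| Label | Lead 1 | Lead 2 | Lead 3 | Pooled |
|---|---|---|---|---|
| 'Day 1' (7 − k) | 6 | 5 | 4 | 4 to 6 |
| 'Day 4-6' | 2, 3, 4 | 1, 2, 3 | 7 (pre-dose), 1, 2 | 1 to 4, or 7 |
| 'Day 9' (8 − k) | 7 | 6 | 5 | 5 to 7 |

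**Step 3: apply the Visit 4 range.** Three doses × three leads × three visit days = 27 combinations. Four fall outside Days 24 to 39: insertion Day 19 sampled on Days 22 and 23, insertion Day 20 sampled on Day 23, and insertion Day 35 sampled on Day 40. That leaves 27 − 4 = 23.

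| Days since dose | 1 | 2 | 3 | 4 | 7 (pre-dose) |
|---|---|---|---|---|---|
| Combinations | 4 | 9 | 6 | 2 | 2 |

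The two troughs are insertion Day 26 sampled on Day 29, and insertion Day 33 sampled on Day 36. Both have lead 3 and a visit on CGM day 4. The first-cycle counterpart (insertion Day 19, sample Day 22) is excluded by the range.

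**Step 4: the other two ranges.** CGM days 4 to 6 span Day 19 + 3 = 22 to Day 35 + 5 = 40, against a stated 24 to 39. CGM day 9 spans Day 19 + 8 = 27 to Day 35 + 8 = 43, against a stated 29 to 43. Enforcing the Visit 5 range removes leads 2 and 3 in the first cycle only (Days 28 and 27), so the 5-to-7-day spread at 'Day 9' remains.

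**Step 5: the SAP reference dates.** Day 21 is 21 − 15 = 6 days after a dose. Days 24, 31 and 38 are each 2 days after (doses on 22, 29, 36). Days 29, 36 and 43 are each 7 days after. They match the lead-1 pattern but exclude no sample taken at another interval.

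**Step 6: size of a trough sample (assumed values).** The documents give no inhibition levels. Assume 90% early and 75% at trough, a 15-point difference. A fraction p of 'Day 4-6' samples taken pre-dose lowers that mean by 15p points: 1.5 at p = 10% (13.5 remain) and 3.0 at p = 20% (12 remain). One subject in 15 gives 1.0 point.

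**The case against.** The strongest reply is that the plan is not blind to dosing and that the damage is small. Much of this stands. The nominal schedule of Days 21, 24 and 29 gives 6, 2 and 7 days after dose, a sensible profile, and the SAP reference dates repeat it. Early and late labels stay largely apart: leaving the trough aside, 'Day 4-6' covers 1 to 4 days and meets 'Day 1' only at day 4. What does not stand is that the reference dates cure the mixing, since they act only when there is more than one candidate value.

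Several stronger readings are tempting, and the documents do not support them:

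- *That the middle sample is often a trough.* It needs a 3-day lead, a visit on CGM day 4 and a later-cycle insertion. The 2 of 23 counts permitted combinations; it is not an expected frequency. It also depends on item 8 of Protocol 7.4. Section 8.1.2 repeats the dose-after-tests instruction at every visit for alogliptin only. If trelagliptin were taken first, the sample would be same-day post-dose: a different mixture, not a trough.
- *That real waning could look like no change.* Step 6 shows attenuation, with most of the assumed difference left.
- *That a 2-day lead also yields troughs.* This follows only from Protocol 13.1.3 and the synopsis, which place the sample "during third to fifth day, and ninth day of CGM which is to be performed for 9 days from Day" 21. Appendix A and the SAP say fourth to sixth. That is a separate wording conflict, and it is not used in the counts above.

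**Conclusion.** The point holds in a limited form. Each on-treatment laboratory label in SAP 7.3.1 pools trelagliptin samples from different days since the last dose: 4 to 6, 1 to 4 and 5 to 7 days. The 'Day 4-6' label can also include a 7-day pre-dose sample, in 2 of 23 permitted combinations. The spreads follow from the permitted lead and assume weekly doses on the nominal calendar; the trough further assumes that the drug is withheld until after sampling.

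The consequence is a flattened weekly profile for DPP-4 activity, its inhibitory rate, GLP-1 and GIP, in one arm. How much depends on the mix of leads and visit days actually used, which the plan does not fix. These are 'other' endpoints in an exploratory study, summarised by arm without a between-group estimate. A reader might infer that the primary result is compromised. It is not: the CGM glucose windows are dose-anchored and do not use these samples. The pre-treatment baseline is unaffected too. This is a cheap improvement worth making, not a flaw that threatens the study's main conclusion.

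**What to change.** 1. **SAP 7.3.1.** For trelagliptin, alongside the CGM-day table, add a plot of individual values and a summary of DPP-4 activity, inhibitory rate, GLP-1 and GIP by actual days since the last dose. Group adjacent days where cells are small. Flag any pre-dose sample and do not average it into 'Day 4-6'.
2. **Data capture.** Record the date of the dose before sensor insertion. It is needed for every 'Day 1' sample and any pre-dose middle sample, but the subject diary (Protocol 9.1.9) runs only during CGM, and the dosing times confirmed under Protocol 9.2 are also those during CGM.
3. **Reconcile the text.** Bring the synopsis and Protocol 13.1.3 (third to fifth day) into line with Appendix A and the SAP (fourth to sixth day), or the reverse. Reconcile the Visit 4 and Visit 5 ranges with the Visit 3 range of Days 19 to 35. Which visit rule is right is for the sponsor to settle.

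Cost: one extra date to collect, small numbers per post-dose day (about 15 subjects over up to seven possible days), and modest extra programming. No added visit or sample is needed.

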7.3.2. Relationship Between Secondary Endpoints and Covariate

Analysis Set: Full Analysis Set

Analysis Variables: AUC over time when blood glucose 110 mg/dL is observed during the 3 hour time period after breakfast

AUC over time when blood glucose 140 mg/dL is observed during the 3 hour time period after breakfast

AUC over time when blood glucose 160 mg/dL is observed during the 3 hour time period after breakfast

AUC over time when blood glucose 180 mg/dL is observed during the 3 hour time period after breakfast

AUC over time when blood glucose 110 mg/dL is observed during the 3 hour time period after lunch

AUC over time when blood glucose 140 mg/dL is observed during the 3 hour time period after lunch

AUC over time when blood glucose 160 mg/dL is observed during the 3 hour time period after lunch

AUC over time when blood glucose 180 mg/dL is observed during the 3 hour time period after lunch

AUC over time when blood glucose 110 mg/dL is observed during the 3 hour time period after evening meal

AUC over time when blood glucose 140 mg/dL is observed during the 3 hour time period after evening meal

AUC over time when blood glucose 160 mg/dL is observed during the 3 hour time period after evening meal

AUC over time when blood glucose 180 mg/dL is observed during the 3 hour time period after evening meal

AUC over time during periods when blood glucose 140 mg/dL is observed

AUC over time during periods when blood glucose 160 mg/dL is observed

AUC over time during periods when blood glucose 180 mg/dL is observed

Cumulative time during periods when blood glucose 140 mg/dL is observed

Cumulative time during periods when blood glucose 160 mg/dL is observed

Cumulative time during periods when blood glucose 180 mg/dL is observed

AUC over time during periods when blood glucose <70 mg/dL is observed

Peak postprandial glucose over time 3 hours after breakfast

Peak postprandial glucose over time 3 hours after lunch

Peak postprandial glucose over time 3 hours after evening meal

Maximum variation of blood glucose over time between before and after breakfast

Maximum variation of blood glucose over time between before and after lunch

Maximum variation of blood glucose over time between before and after evening meal

MAGE

Mean 24-hour blood glucose

Mean daytime blood glucose

Mean nocturnal blood glucose

AUC

AUC over time during periods when blood glucose 110 mg/dL is

observed

SD of 24-hour blood glucose

SD of daytime blood glucose

SD of nocturnal blood glucose

Time Point: Start of the observation period, CGM in treatment period (Day 2, Day 3,

Day 4, Day 5, Day 6, Day 7, Day 8)

Covariate: HbA1c at start of the observation period (NGSP) (%)

[Continuous variable]

SD of 24-hour blood glucose at start of the observation period

[Continuous variable]

Age (years old)

[Continuous variable]

Analysis Methods: For the above analysis items, the following analysis is performed

(1) Correlation coefficients between secondary endpoints and covariates will be calculated by time Point.

7.3.3. Individual Profiles of Blood Glucose Obtained from CGM

Analysis Set: Full Analysis Set

Analysis Variables: Blood Glucose Obtained from CGM

Time Point: CGM in treatment period (Day 2, Day 3, Day 4, Day 5, Day 6, Day 7, Day 8)

Analysis Methods: For the above analysis items, the following analysis is performed

(1) The time course will be presented graphically by subject by treatment group.

7.3.4. Effect on mean 24-hour blood glucose

Analysis Set: Full Analysis Set

Analysis Variables: Change from start of the observation period of mean 24-hour blood glucose

Covariate: HbA1c (NGSP) at start of the observation period (%)

[Continuous variable]

SD of 24-hour blood glucose at start of the observation period

[Continuous variable]

Age (years old) $[< 65, 65 \le Max]$

Background Factor:

Gender [Male, Female]

Height (Start of the observation period) (cm) [Continuous variable]

Weight (Start of the observation period) (cm) [Continuous variable]

BMI (Start of the observation period) (kg/m²) [Continuous variable]

Smoking Classification [Never Smoke, Current Smoker, Ex-Smoker]

Drink Alcohol Almost Every Day? [Yes, No]

Duration of Diabetes Mellitus (Years) [Continuous variable]

HbA1c (NGSP) (Start of the observation period) (%)

[Continuous variable]

Time Point : CGM in treatment period (Day 2, Day 3, Day 4, Day 5, Day 6, Day 7, Day 8)

Analysis Methods: For the above analysis items, the following analysis is performed

- (1) To estimate parameter estimates of background factors and its confidence intervals, ANCOVA will be performed by background factor using change from start of the observation period of mean 24-hour blood glucose as a dependent variable, treatment group as an independent variable, HbA1c (NGSP) and SD of 24-hour blood glucose at start of the observation period, age and each background factor as covariates.
- (2) Perform the same analysis as (1) with the covariate including the treatment group \times each background factor (one factor).

7.3.5. Proportion of Frequency for Blood Glucose Obtained from CGM

Analysis Set: Full Analysis Set

Analysis Variables: Blood glucose level obtained by CGM

Time Point: Start of the observation period, CGM in treatment period (Day 2, Day 3, Day 4, Day 5, Day 6, Day 7, Day 8)

Analysis Methods: For the above analysis items, the following analysis is performed

 Calculate proportion of frequency and graphically show distribution of the data using proportion of frequency as vertical axis and blood glucose level as horizontal axis.

